6.2 Dosage, Preparation and Administration of Study Intervention (HPS)^{250, 251}

HPS will be administered through a cannula placed in a large peripheral vein. All participants will already have a peripheral cannula in place for maintenance fluid replacement. Dosage and adjustments in infusion rates will be administered per Standard Operating Procedures.

The HPS saline bag will be connected to a volumetric infusion set. Based on the weight of the subject, and the current sodium concentration, the appropriate amount of HPS will be placed in the chamber and the tubing attached to the secondary port of the intravenous line already in use for delivery of maintenance fluids. Only the amount of fluid to be installed in the current intervention will be delivered to the chamber, to avoid the possibility of overdose.

The HPS loading dose will take place over a 30-minute period, with duration regulated by adjustment of the drop rate. Maintenance fluids will continue during the infusion of the HPS loading dose to minimize the possibility of phlebitis.

After the loading dose is complete, the infusion rate will be reduced to the maintenance infusion rate (see Standard Operating Procedure).

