6.3 Modification of Study Intervention for a Participant (HPS)

Although sodium abnormalities are rare in CM, in the event that a participant has a (Na⁺) level of > 150 mmol/L on admission, the initial bolus will be deferred and the sliding scale dosing detailed in Table 3 will instead be followed.

The subsequent dosing of HPS is planned on a sliding scale, with the goal of maintaining serum sodium levels between 150 and 160 mmol/L. Serum sodium levels will be checked every 3 hours for the first 12 hours of the study, and then every six hours, unless designated otherwise (Table 3).

Table 5. Dosing schedule for hypertonic saline

Serum Sodium	Dose of 3% HPS	Sodium recheck
< 145 mmol/L	5 mL/kg (bolus)*	3 hours
145 – 150 mmol/L	2 mL/kg (bolus)*	3 hours
150 - 160 mmol/L	None	6 hours
>160 mmol/L	Hold infusion until serum sodium is ≤ 155, restart at 0.5 mL/kg/hr	1 hour

*If > 3 boluses are required to maintain serum sodium between 150-160, then increase infusion by 0.25 mL/kg until no further boluses are required.

Further modifications to the HPS dose will be made in the event of the following laboratory abnormalities (electrolyte abnormality grading detailed in Appendix B):

- Grade 4 hypokalemia (see Toxicity Table in Appendix B)
- A pH drop of more than 0.2 within 6 hours
- Chloride > 125 mmol/L
- Serum osmolality > 340 mOsm

In these instances, planned HPS doses will be held, and corrective actions (detailed in Section 9.2.4) will be taken. Electrolytes will be rechecked in 3 hours and the normal dosing schedule will be reinstated if electrolytes are no longer in the Grade 4 toxicity range.

If the pH < 7.25 or falls by 0.2 within 6 hours or if the serum chloride is > 125 mmol/L, the 3% saline infusion will be stopped and converted to a 1:1 ratio of 3% sodium chloride/sodium acetate solution.

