9.2.3.1 Protocol defined SAEs

CM is a disease with a high mortality rate. Reported mortality rates range from 15 – 30%, with our site having a rate of 18% over the past 25 years. We anticipate the mortality rate in randomization arm 3 will be approximately 37%. All deaths not attributable to the malarial illness will be reported to independent safety monitors, IRBs, and the sponsor as required.

- Death not caused by respiratory arrest secondary to intracranial hypertension.
- Prolongation of existing hospitalization for more than 7 days due to an intervention.
- A life-threatening adverse event that is not part of the study outcomes defined in the study objectives, an attributable to an intervention.

9.2.4 Procedures to be Followed in the Event of Abnormal Laboratory Test Values or Abnormal Clinical Findings

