9.2.4.1 Hypernatremia

Table 3 (Section 6.1.5) categorizes the possible serum sodium levels and actions to be taken if they are observed. A serum sodium measurement of greater than 190 mmol/L will be considered an SAE and reported as such. The 3% HPS infusion will be stopped. Maintenance fluid infusion will continue at maintenance rate. Sodium will be rechecked hourly until its serum level is < 160 mmol/L and therapy will be resumed as per Table 3.

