9.2.4.2 Hypokalemia

As per the toxicity table attached as Appendix B, a serum potassium measurement of <2.0 mmol/L will be defined as a Grade 4 adverse event. Corrective action will be in the form of adding 40 mmol/L of KCl to the maintenance IV fluids (an increase from the 17mmol/L K⁺ present in ½ Strength Darrow’s). IV fluid infusion rate will remain the same. HPS boluses will continue, and electrolytes will be monitored at 3 hour intervals until K⁺ returns to below Grade 3 disturbances.

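### Three of the four laboratory holds on hypertonic saline in Section 6.3 have no release threshold tied to the value that triggered them

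*Combined protocol and SAP*

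**What the plan says.** Section 6.3 sets out a sliding scale for 3% saline driven by serum sodium (Table 5). It then lists four further laboratory findings that modify dosing: Grade 4 hypokalemia, a fall in pH exceeding 0.2 over 6 hours, chloride above 125 mmol/L, and osmolality above 340 mOsm. For these, "planned HPS doses will be held, and corrective actions (detailed in Section 9.2.4) will be taken". Electrolytes are rechecked at 3 hours, and "the normal dosing schedule will be reinstated if electrolytes are no longer in the Grade 4 toxicity range".

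The next paragraph applies when pH is below 7.25, when pH falls by 0.2 in 6 hours, or when chloride exceeds 125 mmol/L. In those cases "the 3% saline infusion will be stopped and converted to a 1:1 ratio of 3% sodium chloride/sodium acetate solution". Osmolality is not mentioned there.

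Sodium has its own rules. Above 160 mmol/L, Table 5 says: "Hold infusion until serum sodium is ≤ 155, restart at 0.5 mL/kg/hr". After a sodium above 190, Section 9.2.4.1 says: "Sodium will be rechecked hourly until its serum level is < 160 mmol/L and therapy will be resumed as per Table 3" (the table now numbered 5).

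Section 9.2.4 is titled "Procedures to be Followed in the Event of Abnormal Laboratory Test Values or Abnormal Clinical Findings". It contains entries for hypernatremia, hypokalemia and phlebitis only. Section 6.2 adds: "Dosage and adjustments in infusion rates will be administered per Standard Operating Procedures".

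**The concern.** A hold should end when the problem that caused it has cleared. The sodium rules work that way. The four further holds instead share a test written in toxicity grades, and three of their triggers have no grade. For those three, the stated test can be met whatever the triggering value is.

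This is a dosing-safety rule for comatose children. Section 2.2.2.4.3 itself names acidosis with high chloride as a recognised effect of hypertonic saline that needs close monitoring. A clinician applying the release sentence alone could restart 3% saline while the abnormality that stopped it persists.

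**Working it through.** The plan gives no figure to reproduce. The check sets each trigger beside the release test, and then asks what dose could follow.

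**Step 1: what Grade 4 covers.** Appendix B's Grade 4 laboratory limits are sodium above 191, potassium above 7.0 and potassium below 2.0 mEq/L. Section 9.2.4.2 agrees on the last: "a serum potassium measurement of <2.0 mmol/L will be defined as a Grade 4 adverse event". There is no row for pH, chloride or osmolality. The release test is therefore met whenever sodium is at most 191 and potassium is 2.0 to 7.0.

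**Step 2: trigger by trigger.**

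| Hold trigger (6.3) | Grade in Appendix B? | Entry in 9.2.4? | Other action in 6.3? | Release value on the trigger? |
|---|---|---|---|---|
| Grade 4 hypokalemia | Yes, below 2.0 | Yes | – | Yes |
| pH fall above 0.2 in 6 h | No | No | Acetate conversion | No |
| Chloride above 125 | No | No | Acetate conversion | No |
| Osmolality above 340 | No | No | None | No |

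The release test matches the trigger for 1 of 4 holds. Some corrective action exists for 3 of 4 once the acetate conversion is counted; osmolality has none.

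**Step 3: a chloride illustration, using the release sentence alone.** Suppose the 3-hour recheck shows chloride 128, sodium 147 and potassium 3.2 mmol/L. No value is Grade 4, so the test is met. Table 5 then gives 2 mL/kg of 3% saline at sodium 145–150. Assuming NaCl at 58.44 g/mol (not in the documents):

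- 30 g/L ÷ 58.44 = 0.513 mmol of chloride per mL.
- 2 mL/kg × 0.513 = 1.03 mmol/kg.
- The 5 mL/kg bolus at sodium below 145 would carry 5 × 0.513 = 2.57 mmol/kg.
- If boluses were also 1:1 acetate at equal strength (assumed), these halve to 0.51 and 1.28 mmol/kg.

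**Step 4: how wide the osmolality gap is.** Assume osmolality = 2 × sodium + glucose + urea, all in mmol/L. To exceed 340, glucose + urea must be above:

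- sodium 150: 340 − 300 = 40
- sodium 155: 340 − 310 = 30
- sodium 160: 340 − 320 = 20

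Below 150, where Table 5 orders boluses, the sum must exceed 40 by still more. From 150 to 160 Table 5 orders no bolus, and above 160 it holds the infusion. What remains is a background infusion at sodium 150–160. Its maintenance rate is in the SOP. The only rate in the document, 0.5 mL/kg/hr, is the restart rate after a sodium hold. At that rate the load is 0.5 × 0.513 = 0.26 mmol/kg of sodium per hour, or 1.54 mmol/kg over the 6-hour recheck interval.

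**The case against.** The strongest reply is that the triggers are standing. A chloride of 128 at recheck is still above 125, so the hold applies again, and a Table 5 bolus is a planned dose. On that reading the bolus in Step 3 is withheld, and the acetate paragraph stops the 3% infusion anyway. This is a fair reading, and Step 3 shows only what the release sentence permits when taken alone. It does not rescue the wording. The Grade 4 sentence would then do no work for three triggers. It also fits pH poorly: that hold trigger is a change within 6 hours, so a pH that fell and stayed low stops meeting it once the window has moved past the fall. The absolute limit of 7.25 appears only in the conversion paragraph.

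A second reply is that these children are closely monitored. Section 4 schedules acid-base status and electrolytes every 3 hours on the first day in this arm, then every 6 hours. A reader might infer that the holds are lifted with nothing measured. The documents do not support that for pH, and probably not for chloride. What is missing is the threshold. Osmolality is weaker: no scheduled measurement appears in Section 4, Sections 8.1 and 8.2.1, or Appendix A.

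Third, the SOP cited in Section 6.2 may hold restart values. It may, but an SOP should not have to override an explicit protocol rule.

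A reader might also infer that every HPS hold in Section 6.3 ends on a Grade 4 test. That is not so: the sodium hold above 160 ends at 155 or below.

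**Conclusion.** The mismatch is certain: three of the four further-modification holds have no release threshold tied to their trigger, and Section 9.2.4 does not supply what Section 6.3 cites it for. For pH and chloride the gap is partial. The acetate conversion probably governs the infusion, but it is not reconciled with reinstating the normal schedule, has no return value, and is silent on Table 5 boluses. For osmolality the gap is complete but narrow.

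The consequence for dosing is uncertain. It depends on whether the triggers are read as standing and on an SOP not provided. The stronger conclusion, that the protocol requires 3% saline to be restarted at a chloride or osmolality still over its limit, is not supported; that is one literal reading among others. The dose figures rest on the assumed molar mass, acetate strength and osmolality formula. They show possible doses, not how often the problem would arise. The primary analysis is unaffected. This is a minor safety-wording correction.

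**What to change.** In Section 6.3, recheck the triggering value itself at 3 hours and restart only when it has cleared:

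- chloride at or below 125 mmol/L;
- osmolality at or below 340 mOsm;
- potassium at or above 2.0 mmol/L;
- pH at an absolute value, for example 7.25 or above (the limit Section 6.3 already uses for conversion), subject to clinical confirmation. A fall above 0.2 from a pH above 7.45 can leave pH at or above 7.25 (7.45 − 0.2 = 7.25), so the clinical team should say what else is needed in that case.

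State that the acetate conversion governs for pH and chloride, whether it covers Table 5 boluses, and when 3% saline may return. Correct the Section 9.2.4 reference, either by adding the missing actions there or by pointing to the SOP if it holds them.

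The cost is wording in Section 6.3 and one cross-reference. Sample size and analysis do not change. Section 9.2.4.2 continues boluses in Grade 4 hypokalemia while Section 6.3 holds them; that is a separate conflict, but it could be settled in the same edit.

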6.4 Accountability Procedures for the Study (Intervention/Investigational Product(s) (HPS)

Based on the anticipated recruitment for a calendar year, supplies will be ordered according to anticipated need and in accordance with expiration dates. Bags will remain stored in the storage case in the locked cabinet in the pharmacy until needed on the ward. On enrollment of a participant a bag will be brought to the ward for initiation of therapy. Removal from the pharmacy will be documented on a product inventory log. The lot number and expiration date of the bag will be recorded on the participant CRF. Bags will not be shared between participants. At the end of the calendar year or when the expiry date is reached (whichever comes first), the remaining product will be discarded.

6.5 Assessment of Subject Compliance with Study Intervention/Investigational Product (HPS)

HPS will be administered by dedicated, trained study nurses, with appropriate documentation. Any irregularities in administration will be recorded and reported as a protocol deviation.

6.6 Study Product Description – Ventilatory Support

6.6.1 Acquisition

Age-appropriate mechanical ventilators will be used in at the bedside in the PICU; an MRI-compatible ventilator will be used to address transport needs of study subjects from the PICU to the MRI suite.

6.6.2 Formulation, Packaging, and Labeling

NA

6.6.3 Product Storage and Stability

NA

6.7 Dosage, Preparation and Administration of Study Intervention/Investigational Product (VENT)

Mechanical ventilation will be initiated immediately after randomization to Study Arm 1, or in the event of a respiratory arrest for subjects allocated to Arms 2 and 3.

Endotracheal intubation will be performed by a pediatric intensivist after administration of IV anesthetic agents in doses described in the sedation section (Section 6.3). The size of the endotracheal tube to be used for each patient will be determined by the pediatric intensivist on-site using standard formulas. A variety of sizes of both cuffed and uncuffed endotracheal tubes will be available (ranging from size 3.0 to 7.5) along with laryngoscopes and different sizes of blades

At the discretion of the intensivist, initial ventilator settings may be set to deliver a Tidal Volume at 6-8 ml/kg, age-appropriate respiratory rate, Peak End Expiratory Pressure of 5 and Fraction of Inspired Oxygen at 40%. The settings will be adjusted by the pediatric intensivists to target a pCO₂ (partial pressure of carbon dioxide) in arterial blood of 35-40 mmHg and maintain oxygen saturation above 90% on pulse oximetry.

At the discretion of an intensivist, an arterial line may be placed in the ventilated subjects to measure arterial blood gases every 3 hours for the first 24 hours and every 6 hours subsequently until the participant is extubated.

Participants will remain intubated until brain volume has decreased (brain volume score \leq 6) and the participant has improved clinically (modified Blantyre Coma Score \geq 3) or the patient has improved clinically (modified Blantyre Coma Score \geq 4, no repeat MRI needed) or the patient dies or develops severe irreversible neurologic damage or for a maximum of 7 days.

Intubated participants will be moved from side to side every 2 hours (\pm 1 hour) to reduce chances of bed sores. If tolerated, they will undergo endotracheal suctioning every 6 hours (\pm 2 hours) and more often as needed to prevent plugging of the endotracheal tube by mucoid secretions, using an appropriate sized suction catheter attached to wall suction. Participants may be pre-medicated prior to suctioning using sedation medications described in section 6.3.

Participants will receive chest physiotherapy as needed if they develop evidence of lung atelectasis. They may be premedicated with sedation medications as described in section 6.3.

6.8 Modification of Study Intervention/Investigational Product for a Participant (VENT)

In the event that a participant develops a nosocomial pneumonia, appropriate broad-spectrum antibiotics will be initiated after respiratory cultures are sent. Antibiotics will be continued until clinical improvement is noted or for a duration determined by the pediatric intensivist.

In the event of accidental tube dislodgement, participants will be reintubated by the pediatric ICU staff under the guidance of the intensivist.

In the case of a pneumothorax, at the discretion of an intensivist a chest tube may be inserted and hooked to suction to aid lung re-expansion.

In the case of hypotension resulting from positive intrathoracic pressure from mechanical ventilation or secondary to use of sedative agents, participants may receive a 10-20 ml/kg fluid bolus using normal saline or Ringer's lactate, at the discretion of the intensivist.

Participants at risk for development of post-extubation stridor (those with a traumatic or with multiple intubations), will be eligible to receive a 4-dose course of dexamethasone IV prior to planned extubation. In case of stridor noted after extubation, nebulized racemic epinephrine will be administered as needed, at the discretion of the intensivist.

6.9 Accountability Procedures for the Study Intervention (VENT)

NA

6.10 Assessment of Subject Compliance with Study Intervention (VENT)

NA

6.11 Concomitant Medications/Treatments

While on the PICU/PRW, all participants will receive standard of care anti-malarial treatment. This includes the following:

- Anti-malarial treatment: Artesunate will be administered according to national treatment guidelines upon admission, at 12- and 24-hours post-admission, and once a day thereafter until the child is able to take oral medication, or for a total of 5 days. After the child is able to take oral medications, they will be prescribed Co-Artem® (a fixed dose combination tablet containing artemether, 20 mg and lumefantrine, 120 mg). Dosing will be weight-based according to national treatment guidelines. Oral therapy is for three days.
- Antipyretics: An aggressive fever control regimen will be undertaken in both arms – as pyrexia has been shown to be a major predictor of poor outcome in TBI participants²⁵². Anti-pyretic therapy will be initiated for any temperature $>38^{\circ}\text{C}$. The two components will be:
 - Paracetamol – 25mg/kg per rectum (PR) loading dose and 15 mg/kg PR Q6 hours thereafter
 - Ibuprofen – 10mg/kg per naso-gastric tube (PNGT) Q6 hours

Therapy will be initiated with paracetamol. If euthermia is not achieved in 3 hours, ibuprofen will be added. The two modalities may be scheduled on alternating Q6 hour regimens, at the discretion of the intensivist.

- Anti-convulsants: Locally available anti-convulsants include paraldehyde, diazepam, phenobarbital, and phenytoin. Choice of a specific anti-convulsant is determined on a participant-to-participant basis based on the duration of seizures, available routes of administration, and other clinical characteristics (e.g., respiratory status) of the participant.
- Antibiotics: Participants initially unable to undergo lumbar puncture to rule out meningitis will be placed on ceftriaxone (100mg/kg IV, daily) until a lumbar puncture can be performed or for a maximum of seven days, whichever comes first. A blood culture will be collected initially on all patients, and appropriate antibiotics will be prescribed on the basis of a positive culture. Participants with fever refractory to anti-malarials will have a second venous blood sample collected for culture and the initiation of empiric antibiotic treatment until culture results are available. Continued antibiotic administration will be dependent on blood culture results and clinical status. See Section 6.2.5 for antibiotic therapy for intubated patients who develop a nosocomial pneumonia.
- Sedation: Participants requiring ventilator support will be intubated after induction of anesthesia with ketamine IV ²⁵³ along with diazepam. Atropine will be available in case of bradycardia associated with direct laryngoscopy. While patients remain intubated, they may be pre-treated (at the discretion of the intensivist) with morphine or diazepam or lidocaine prior to noxious stimulation such as endotracheal tube suctioning or placement of gastric tubes, intravenous lines, etc.
- Fluids/Nutrition:
 - At admission, all participants will be placed on maintenance fluids
 - Infusion rates will adhere to the QECH Dept. of Paediatrics protocol: 4mls/hr for the first 10kg, 2ml/hr for next 10kg, 1ml/hr for any weight above 20kg. Adjustments may be performed at the discretion of the intensivist.
 - If a participant remains comatose and is therefore unable to take oral feeds at 36 hours post-randomization, a nasogastric tube will be placed, and a milk-based nutritional supplement will be administered at the same rate as peripheral IV fluids. IV fluids infusion rates will be decreased as NG feed volumes are increased. Nasogastric feeds will be initiated when deemed safe by the PICU physician.
 - 50% Dextrose will be used as a rescue therapy for subjects experiencing hypoglycemia of < 3.0 mmol/L.
- Blood transfusions will be administered as required on clinical grounds.
- Oxygen therapy: Oxygen saturation will be measured continuously in the PICU; it will be measured and recorded on the PRW every two hours by a dedicated study nurse using a portable oxygen monitor with a pediatric finger probe. From the TBI literature adequate

oxygenation is important for treating raised intracranial pressure as injured tissue is highly susceptible to secondary insults including hypoxia²⁵⁴⁻²⁵⁶. Supplemental oxygen will be provided by nasal cannula, endotracheal tube, or mask to maintain peripheral oxygen saturations above 90%.

- Chloral hydrate: Chloral hydrate will be used in children returning for 1-month follow-up visits if sedation is required for the follow-up MRI.
- Omeprazole: Omeprazole may be added at the intensivist's discretion should any participants experience gastrointestinal bleeding. Study Schedule

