8 STUDY PROCEDURES/EVALUATIONS

8.1 Clinical Evaluations

History: A brief medical history pertaining to the immediate clinical condition is obtained immediately on arrival to the PRW. More detailed medical history is obtained after the participant has been stabilized. History includes a history of the immediate illness, previous similar illnesses, and a brief developmental history. History is obtained by interview and supplemented by any records in the participant's health passport.

Medication history is obtained on admission to the PRW and recorded on the same enrollment form. This history relies heavily on the written record provided in the health passport of the participant.

Physical Examination: A full physical examination is performed on arrival to the PRW and after immediate stabilization. Specific vital signs and organ systems evaluated can be found on the physical exam CRF). Twice daily after consent, a targeted physical exam is conducted by a study physician. The results of these daily examinations are recorded in free form on the continuation sheets. At minimum these exams will evaluate the neurologic status of the participant (as determined by BCS), examination of the heart, lungs, liver, and spleen.

Vital Signs: Vital signs (temperature, pulse rate, blood pressure, respiratory rate, oxygen concentration, and BCS) will be evaluated and recorded by a dedicated study nurse every two hours until the participant regains consciousness (BCS \geq 3).

Table 6. Blantyre Coma Score (maximum = 5):

Motor Response	Verbal Response	Eye Movements
Nil/extend	0	Nil/gasp 0
Withdraw	1	Abnormal cry 1
Localize	2	Normal cry or speech 2

Table 7. Modified Blantyre Coma Score (for intubated patients, maximum = 5):

Motor Response	Verbal Response	Eye Movements
Nil/extend	0	Nil/gasp 0
Withdraw	1	Attempt to cry, grimace 1
Localize	2	Clear mouthing of words around ET tube 2

IV anti-malarial therapy: Artesunate will be administered according to national treatment guidelines upon admission, at 12- and 24-hours post-admission, once a day thereafter until the child is able to take oral medication, or for a total of 5 days.

Oral anti-malarial therapy: After the child is able to take oral medications, they will be prescribed Co-Artem® (a fixed dose combination tablet containing artemether, 20 mg and lumefantrine, 120 mg). Dosing will be weight-based, in accordance with national treatment guidelines. Oral therapy is for three days.

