Appendix A

Schedule of Events

Clinical and Laboratory Evaluations

A = performed on all children on PRW/PICU [(A) = only if still unconscious]

S = performed on children eligible to be screened for TBS study

I = performed as part of TBS trial [(I) = only if still unconscious]

Event	Admission	Screening	With TBS consent	Day 1	Day 2	Days 3 -7	Follow-up visits
History	A						A
Physical Exam	A			A,A	A,A	A,A	A
Vital signs	A			A – q2 hours	A – q2 hours	A – q2 hours	A
IV anti-malarial Rx	A			A,A	A,A		
PO anti-malarial Rx						A (3 day course)	
MP and PCV	A			A A A A	(A)(A) (A)(A)	(A)(A) (A)(A)	A
Lactate and glucose check	A			A A A A	(A)(A) (A)(A)	(A)(A) (A)(A)	
Lumbar Puncture	A						
Retinal exam		S		(I,)	(I,)	(I,)	
MRI		S		I	(I)	(I)	I (1 month)
NIRS		S		I	I	I	I (1 month)
TCD		?	I?	I	I	I	I (1 month)
ONSD			I	I,	(I,)	(I,)	I
Expanded neurologic exam			I	I, I	(I,I)	(I,I)	I
Heart rate variability			I	I	I	I	
Lung ultrasound			I	I	I	I	
Brain swelling intervention			I	I	I	I	

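### Appendix A contradicts Sections 6.11 and 8.1 on antimalarial treatment: IV frequency on Day 2, IV treatment after Day 2, and the condition for changing to oral treatment

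*Combined protocol and SAP*

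**What the plan says.** Section 6.11 makes antimalarial treatment part of background care in every arm: "While on the PICU/PRW, all participants will receive standard of care anti-malarial treatment". It times artesunate "upon admission, at 12- and 24-hours post-admission", and then "once a day thereafter until the child is able to take oral medication, or for a total of 5 days". The change to oral treatment depends on the child's ability to take it: "After the child is able to take oral medications, they will be prescribed Co-Artem", for three days.

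Section 8.1 repeats this timing and names the route: "IV anti-malarial therapy: Artesunate will be administered according to national treatment guidelines upon admission". The two sections agree with each other.

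Appendix A has two relevant rows.

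- "IV anti-malarial Rx": one entry at admission, two on Day 1, two on Day 2, and a blank cell for Days 3-7.
- "PO anti-malarial Rx": a single entry, in Days 3-7, for a three-day course.

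The legend explains the codes: "A = performed on all children on PRW/PICU [(A) = only if still unconscious". Both antimalarial rows use the plain code only, so as written they apply to all children.

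**The concern.** The protocol gives two different schedules for the core background treatment of all three arms. They differ on how often IV treatment is given on Day 2, on whether it exists after Day 2, and on what triggers the change to oral treatment. In the text the trigger is the child's ability to take oral medication. In Appendix A it is the day number.

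The population makes this more than a matter of form. Children enter with a Blantyre Coma Score of 2 or less, and Arm 1 may be ventilated for up to 7 days. Appendix A itself expects some children to be unconscious in Days 3-7. It uses the bracketed code there for parasitemia and hematocrit, lactate and glucose, and it brackets the retinal, MRI, optic nerve sheath and neurologic rows in the same way. The antimalarial rows do not use that code.

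There is also a compliance cost. Section 15.6 treats any noncompliance with the protocol as a deviation. Where the two schedules differ, staff who follow one depart from the other.

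**Working it through.** No power or error-rate figure is involved. The check is whether the conflict survives a fair reading of the table.

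**1. Is it a column shift from text extraction?** Each antimalarial row has 8 cells against 8 header columns (event, admission, screening, trial consent, Day 1, Day 2, Days 3-7, follow-up). The blank cell does belong to Days 3-7.

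**2. Does A,A mean twice in the day?** Two other rows can be compared with Section 8.1. The physical examination row reads A,A, and Section 8.1 specifies that examination twice daily. The parasitemia and hematocrit row has four entries on Day 1, and Section 8.1 specifies every six hours. Entries therefore count occasions per day.

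**3. Does the conflict depend on how days are numbered?** The text gives doses at 0, 12, 24, 48, 72 and 96 hours (6 doses), or also at 120 hours (7 doses) if five days is counted that way. The last column below assumes a child who cannot take oral medication throughout.

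| Day numbering | Text: Day 2 | Text: to end of Day 2 | Text: after Day 2 |
|---|---|---|---|
| Admission dose separate; Day 1 is the next 24 h | 1 (48 h) | 4 | 2 or 3 |
| Day 1 is the first 24 h, including admission | 1 (24 h) | 3 | 3 or 4 |
| First 24 h is Day 0 | 1 (48 h) | 4 | 2 or 3 |
| Calendar days, admission day is Day 0 | 1 (48 h) | 4 | 2 or 3 |
| Calendar days, admission day is Day 1 | 1 if admitted before noon, otherwise 2 (12 h and 24 h) | 3 | 3 or 4 |
| **Appendix A** | **2** | **1 + 2 + 2 = 5** | **0 IV** |

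The last column is 6 or 7 minus the running total: 6 − 4 = 2 at the lowest, 7 − 3 = 4 at the highest.

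In one case the Day 2 cell could match the text: calendar days with admission as Day 1, for a child admitted at noon or later. The earlier cells then disagree instead, because the text gives one dose on the admission day against 1 + 2 = 3 in Appendix A. The total to the end of Day 2 differs under every numbering (3 or 4 against 5), and so does IV treatment after Day 2.

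**4. Does the condition for changing to oral agree?** No. The text continues IV treatment until oral medication is possible, within the five-day limit. Appendix A marks IV for all children on Day 2 and oral for all children in Days 3-7. It therefore conflicts with the text in both directions: for a child who can take oral medication by Day 2, and for one who still cannot on Day 3.

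**The case against.** The strongest reply is that Appendix A is not the dosing instruction. It sits under a heading for clinical and laboratory evaluations. Sections 7.2 and 7.4 cite it for evaluations and Section 8.3.5 for spectroscopy timing; no section cites it for antimalarial dosing. It is also visibly rough, with question marks left in the transcranial Doppler row. This stands in part: it is a reason not to treat each cell as a dose order. It does not remove the conflict. Section 8.1 is itself headed Clinical Evaluations and contains the IV and oral antimalarial paragraphs, and the first ten rows of Appendix A follow its order. The table therefore contradicts the section it summarises, and the available text gives no rule on which prevails.

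A reader might go further and infer three things that the documents do not support.

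- *A child comatose or ventilated on Day 3 has no scheduled antimalarial that can be given.* This is true only of Appendix A read alone, since Sections 6.11 and 8.1 schedule artesunate for that child. Nor is it settled that no enteral route exists. Section 6.11 plans a nasogastric tube for feeds in children still comatose at 36 hours after randomization and gives ibuprofen by that route. It does not say that antimalarials go that way.
- *The gap would fall mainly on the ventilation arm and confound the mortality comparison.* This supposes that staff would follow the table over the text, and no figure supports that. Prolonged coma can occur in any arm, and children in Arms 2 and 3 are ventilated after respiratory arrest. Ventilation on Days 6-7 does not widen the gap as such, because the text limits artesunate to five days in total.
- *The number of affected children can be estimated.* Section 2.3 says 85% have died or been discharged by 72 hours, but the rest are children in hospital, not children unable to take oral medication. Projecting from the 20.5-hour placebo median in the Ugandan mannitol trial (Section 2.2.2.4.2) would assume an exponential shape. It would also borrow from quinine-treated children who are not described as selected for brain swelling.

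**Conclusion.** The contradiction is real and the plan is wrong as written on this point. By the end of Day 2 Appendix A shows five IV entries against three or four doses in the text. After Day 2 it shows none, against two to four for a child unable to take oral medication for the full five days. The change to oral treatment follows the calendar in one place and the child's condition in the other. The counts assume that each entry is one dose, which the other rows of the same table support.

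The consequence is limited. The protocol as a whole does provide for a child still comatose on Day 3; the risk arises if someone works from the Schedule of Events alone. The documents do not show that any child would go untreated or that the comparison between arms would be biased. This is an internal inconsistency about core background therapy, relevant to safety and to the recording of deviations. This review takes no view on which schedule is right.

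**What to change.** Reconcile the IV and oral antimalarial rows of Appendix A with Sections 6.11 and 8.1. Three items should agree in all three places: the frequency on Day 2, coverage after Day 2, and the condition for changing from IV to oral. Appendix A should also state how its days are numbered relative to admission, since the text times the first doses in hours from admission. The clinical team decides which schedule is correct and whether the table or the text changes.

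The cost is an edit to two table rows and a footnote, or to two paragraphs. No new procedure, data item or analysis is needed.
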